4.0 BACKGROUND & RATIONALE

4.1 Background

Refer to the Investigator's Brochure (IB) for detailed background information on V114.

4.1.1 Pharmaceutical and Therapeutic Background

The investigational Merck pneumococcal conjugate vaccine, hereafter referred to as V114, is a 15-valent conjugate vaccine that contains all 13 pneumococcal serotypes contained in Prevnar 13™ (1, 3, 4, 5, 6A, 6B, 7F, 9V, 14, 18C, 19F, 19A, 23F), and 2 additional pneumococcal serotypes (22F, 33F). The pneumococcal serotypes contained in V114 will provide broader coverage of the current leading serotypes associated with pneumococcal disease worldwide. The vaccine is designed to meet continuing medical and public health global needs for pneumococcal conjugate vaccines as well as to address the emergence of pneumococcal disease caused by serotypes not contained in currently licensed pneumococcal conjugate vaccines. The pneumococcal serotype composition of V114 is based on the need to maintain coverage of the serotypes included in Prevnar 13™, and to add serotypes guided by current epidemiology data and emerging trends [1].

Streptococcus pneumoniae (pneumococcus) is a major worldwide cause of morbidity and mortality and is responsible for more than half of all community-acquired pneumonia (CAP), otitis media, bacteremia and meningitis cases [2]. Bacteremia and meningitis are referred to as invasive pneumococcal disease (IPD). In 2006, the World Health Organization (WHO) estimated that pneumococcus caused the deaths of at least 1.5 million people annually [2]. In 2009, pneumococcus accounted for over 1 million deaths in children <5 years of age, mostly in developing countries [3, 4].

Three licensed pneumococcal conjugate vaccines have been licensed since 2000. The 7-valent Prevnar™, conjugated to diphtheria toxoid mutant (PCV7-CRM197) was first licensed and introduced into national childhood vaccination schedules in the US, European Union (EU), and several other countries. Since then, a 10-valent (PCV10), and a 13-valent (PCV13-CRM197) pneumococcal conjugate vaccine have also been licensed. PCV13-CRM197 was approved in the EU in 2009, the US in 2010, and subsequently in other countries worldwide. The vaccine is licensed globally as Prevnar 13™ and Prevenar 13™, and in this protocol the vaccine will be referred to by the name Prevnar 13™. In 2009 PCV10 marketed as Synflorix™ (pneumococcal 10-valent conjugate vaccine [Non-Typeable *Haemophilus influenzae* (NTHi) protein D, diphtheria or tetanus toxoid conjugates], GlaxoSmithKline Biologicals s.a., Rixensart, Belgium) was licensed in Europe and other countries worldwide. Synflorix™ contains the serotypes contained in Prevnar™ conjugated to 3 different carrier proteins, plus 3 additional capsular polysaccharide conjugates (serotypes 1, 5, and 7F). This vaccine is currently not licensed in the US. According to the US pediatric vaccination schedule, licensed PCV is administered to infants in a 3-dose infant primary series (at approximately 2, 4, and 6 months of age), followed by a toddler (fourth) dose at age 12 to 15 months of age.

PCV7 was highly effective in preventing invasive pneumococcal disease (IPD) caused by the serotypes included in the vaccine in children targeted for the vaccine [5], in providing moderate protection against pneumococcal acute otitis media (AOM) [6] and pneumonia [7]. Widespread use of PCV7 also decreased transmission of pneumococcal disease caused by vaccine serotypes in individuals not targeted by the vaccination program [8, 9]. PCV10 and PCV13 were licensed on the basis of immunogenicity and reactogenicity profiles comparable with that of PCV7. Despite the above mentioned public health benefits of PCV7 [10], serotype replacement emerged as an important public health concern as new serotypes begin to fill the niche created by the suppression of nasopharyngeal colonization of vaccine serotypes [11]. In the US, serotype 19A was, for instance, a leading causative pneumococcal serotype of IPD and respiratory disease several years ago [12, 13]. More recently, IPD cases caused by serotypes 22F and 33F, the 2 additional serotypes contained in V114 (not contained in Prevnar 13TM) have also increased. Although only contributing for 1.2% of all IPD cases in US children under 5 years of age in 1998-1999 [14], IPD caused by these 2 serotypes increased to approximately 9.6% and 29% of IPD cases by 2006-2007 and 2011, respectively [15]. This phenomenon of serotype replacement substantiates the need for the development of more broadly-based pneumococcal conjugate vaccines.

4.1.2 Pre-clinical Trials

Preclinical immunogenicity studies of V114 formulations have been conducted in 2 animal models (refer to the V114 IB).

4.1.3 Clinical Trials

Several clinical trials of a single dose (toddlers, young and older adults) and 4-dose series (infants) of V114 have been conducted to evaluate the safety and immunogenicity of various formulations of V114 containing different amounts of pneumococcal polysaccharide and aluminum adjuvant. Trial results showed that V114 displays an acceptable safety profile and induces serotype-specific antibodies (IgG and OPA) to all 15 serotypes included in the vaccine (See IB for additional information).

4.1.4 Information on Other Trial-Related Therapy

In this trial, Prevnar 13TM will be administered as one of the trial vaccines, to serve as the active comparator. In addition to the administration of trial vaccine (V114 or Prevnar 13TM), other pediatric vaccines will be administered concomitantly according to the recommended schedule for sites in the United States and according to local, regional, and/or country guidelines outside of the United States.

4.2 Rationale

4.2.1 Rationale for the Trial and Selected Subject Population

Safety and immunogenicity of several formulations of V114 containing different concentrations of pneumococcal capsular polysaccharide and aluminum adjuvant were evaluated in small Phase I/II clinical trials involving a small number of adults and infants. The leading formulation displaying acceptable safety profile and optimal immune responses in these studies will be evaluated in a larger number of infants in V114-008. This trial is designed to select the optimal quality attributes of the vaccine contained in either V114 lot to be tested in subsequent phases of V114 clinical development. The trial will enroll healthy infants at approximately 2 months of age, consistent with current recommendation of routine vaccination with PCV in early childhood.

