8.1 Statistical Analysis Plan Summary

Key elements of the statistical analysis plan are summarized below; the comprehensive plan is provided in Sections 8.2-8.11.

Trial Design Overview	A Phase II, Double-Blind, Randomized, Multicenter Trial to Evaluate the Safety, Tolerability, and Immunogenicity of V114 Compared to Prevnar 13™ in Healthy Infants
Treatment Assignment	This is a double-blind trial with three vaccination groups. Subjects will be randomized to V114 Lot 1 (V114-1), V114 Lot 2 (V114-2), and Prevnar 13™ with the ratio 1:1:1.
Analysis Populations	1. Immunogenicity: Per-protocol (PP). 2. Safety: All Subjects as Treated (ASaT)
Primary Endpoints	1. The proportion of subjects meeting serotype-specific IgG ≥ 0.35 $\mu\text{g/mL}$ for the 13 serotypes shared with Prevnar 13™ measured by the Pn ECL assay at 1 month post-dose 3 2. The serotype-specific IgG GMC for all 15 serotypes included in V114 measured by the Pn ECL assay at 1 month post-dose 3
Secondary Endpoint	The serotype-specific IgG GMC for all 15 serotypes included in V114 measured by the Pn ECL assay at pre-dose 4 and 1 month post-dose 4.
Statistical Methods for Key Immunogenicity Analyses	To address the primary objective #2, a V114 formulation will be considered non-inferior to Prevnar 13™ if the lower bound of the two-sided 95% confidence interval (CI) of the between-treatment difference (V114 – Prevnar 13™) in the proportion of subjects with PD3 IgG ≥ 0.35 $\mu\text{g/mL}$ for the 13 serotypes in common between V114 and Prevnar 13™ is > -0.15 . The Miettinen and Nurminen approach [21] will be used. To address the primary objective #3, the within-group IgG GMC along with two-sided 95% CIs will be computed for all 15 serotypes included in V114. Additionally, GMC ratios (V114/Prevnar 13™) along with two-sided 95% CIs will be computed for each of the two V114 lots (V114-1 and V114-2) for all 15 serotypes included in V114. The 95% CI for the ratio will be calculated.

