8.2 Responsibility for Analyses/In-House Blinding

The statistical analysis of the data obtained from this trial will be the responsibility of the Clinical Biostatistics department of the Sponsor.

This trial will be conducted as a double-blind trial without complete in-house blinding procedures. Section 5.2.3 specifies the roles and responsibilities of the site and Sponsor personnel who will be unblinded during the trial. The official, final database will not be unblinded until medical/scientific review has been performed, protocol deviations have been identified, and data have been declared final and complete.

The Clinical Biostatistics department will generate the randomized allocation schedule(s) for trial treatment assignment. Randomization will be implemented using interactive response technology (IRT).

With the exception of the unblinded CRA who will monitor and reconcile the trial vaccine, all other MRL employees directly involved with the conduct of this trial will remain blinded to the subject's treatment assignment until medical/scientific review of all safety and immunogenicity data has been performed, protocol deviations have been identified, and data have been declared final and complete.

The planned interim analysis is described in Section 8.7. The results of interim analysis will not be shared with the investigators prior to the completion of the trial. Subject-level unblinding will be restricted to the internal unblinded statistician and unblinded statistical programmer performing the interim analysis. Group summaries will be reviewed by the Sponsor's trial team in order to make scientific decisions for future studies.

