8.4 Analysis Endpoints

Immunogenicity and safety endpoints that will be evaluated for within- and between-treatment differences are listed below.

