8.6.1 Statistical Methods for Immunogenicity Analyses

The immunogenicity analyses will be conducted for each serotype separately.

For the primary hypothesis, a V114 lot will be considered non-inferior to Prevnar 13™ if the lower bound of the two-sided 95% confidence interval (CI) for the between-treatment difference (V114 - Prevnar 13™) in the proportion of subjects meeting serotype-specific IgG $\geq 0.35 \mu\text{g/mL}$ at 1 month post-dose 3 for the 13 serotypes (1, 3, 4, 5, 6A, 6B, 7F, 9V, 14, 18C, 19F, 19A and 23F) in common between V114 and Prevnar 13™ is >-0.15 (15 percentage point non-inferiority margin). The proposed 15 percentage point provides adequate precision around the primary immunologic endpoints and greater confidence in predicting the outcome of the Phase III pivotal study. The Miettinen and Nurminen approach will be used.

The within-group IgG GMC along with two-sided 95% CIs will be computed for all 15 serotypes included in V114. Point estimates of GMCs are the exponentiated estimates of the mean natural log concentrations. The confidence limits for GMCs are the exponentiated confidence limits for the mean natural log concentrations, based on 1-sample t-distributions. Additionally, GMC ratios (V114/Prevnar 13™) along with two-sided 95% CIs will be computed for each of the two V114 lots (V114-1 and V114-2) relative to Prevnar 13™ for all 15 serotypes included in V114. The 95% CI for the ratio will be calculated using the t-distribution with the variance estimate derived from a linear model utilizing the log-transformed antibody titers as the response and a single term for vaccination group (including the subjects from both V114 lots and Prevnar 13™).

A detailed analysis strategy for immunogenicity endpoints is listed in [Table 3](#).

Table 3 Analysis Strategy for Immunogenicity Variables

Endpoint/Variable (Description, Time Point)	Statistical Method	Analysis Population	Missing Data Approach
Primary Objectives			
Proportion of subjects with PD3 IgG $\geq 0.35 \mu\text{g/mL}$ for the 13 common serotypes between V114 and Prevnar 13™	Non-inferiority of V114 compared with Prevnar 13™, based on difference in percentages (Miettinen and Nurminen)	PP [Primary] FAS [Supportive]	Missing data will not be imputed

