The PD3 IgG GMCs for all 15 serotypes included in V114	
 Within-group GMCs and 95% CI GMC ratio (V114/Prevnar 13™) and 95% CI (t-distribution with the variance estimate from a linear model including the subjects from both V114 lots and Prevnar 13™) 	PP [Primary] FAS [Supportive]	Missing data will not be imputed
Secondary Objectives			
The pre-dose 4 and PD4 IgG GMCs for all 15 serotypes included in V114	
 Within-group GMCs and 95% CI GMC ratio (V114/Prevnar 13™) and 95% CI (t-distribution with the variance estimate from a linear model including the subjects from both V114 lots and Prevnar 13™) 	PP	Missing data will not be imputed
GMC = Geometric Mean Concentration GMFR = Geometric mean fold rise from Day 1. PP = Per-protocol FAS = Full Analysis Set CI = Confidence interval			

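### Does choosing between the two V114 lots require a prespecified Lot 1 versus Lot 2 estimate?

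*Combined protocol and SAP*

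**What the plan says.** The rationale in Section 4.2.1 states the purpose: "This trial is designed to select the optimal quality attributes of the vaccine contained in either V114 lot to be tested in subsequent phases". Section 8.2 has group summaries reviewed by the sponsor's "trial team in order to make scientific decisions for future studies", and Section 8.7 with Table 5 gives the interim analysis the same use.

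The formal objectives are narrower. In Section 3.1, objective 2 tests each lot for non-inferiority to Prevnar 13 and objective 3 asks for per-group GMCs and lot-to-Prevnar 13 ratios. Section 3.2 repeats the GMC objective for pre-dose 4 and post-dose 4. Section 3.3 does the same for the remaining response rates and describes OPA results by group.

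The analyses follow. Section 8.6.1 says "The within-group IgG GMC along with two-sided 95% CIs will be computed for all 15 serotypes included in V114", and that GMC ratios with 95% CIs "will be computed for each of the two V114 lots (V114-1 and V114-2) relative to Prevnar 13". Those ratios come from a linear model with "a single term for vaccination group (including the subjects from both V114 lots and Prevnar 13"; Table 3 repeats "variance estimate from a linear model including the subjects from both V114 lots and Prevnar 13". Section 8.6.2 compares the lots with Prevnar 13 on safety, and Section 8.8 defines success for each lot against Prevnar 13.

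Two phrases are more general. Section 8.4 speaks of "endpoints that will be evaluated for within- and between-treatment differences are listed below", and Section 8.9.2 describes detectable differences between any two groups. Neither names a lot contrast. Section 8.1 says that "the comprehensive plan is provided in Sections 8.2-8.11".

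**The concern.** If a trial exists partly to choose between two lots, one expects a planned estimate of the difference between them with its uncertainty. None is named. The general wording in 8.4 does not supply one, and Table 7 in 8.9.2 lists only V114 against Prevnar 13.

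Three things would be at stake. The team could rank the lots on differences that are no more than chance. It could read one lot passing non-inferiority and the other failing as evidence that the lots differ. And since the two lot-versus-Prevnar 13 intervals share a control group, it might seem that no interval for the lot difference can be obtained from the planned output.

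**Working it through.** **Inputs.** From Section 8.9.1: 350 per group at 85% evaluability, 350 × 0.85 = 297.5, about 298, which matches the plan's figure. Allocation is 1:1:1 (Section 5.3). For 6B the V114 rate is 0.82; the Prevnar 13 rate is 0.80 + 0.07 = 0.87. The documents give no SD for log IgG; I assume 1.0, with a range of 0.8 to 1.2. Table 6 is redacted.

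**1. Is the lot GMC ratio, with its interval, available from planned output?** Write P for Prevnar 13 and s² for the pooled log-scale variance of the three-group model.

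- Point estimate: (L1/P) ÷ (L2/P) = L1/L2.
- Planned log half-width, L1 against P: t·s·√(1/n₁ + 1/n_P).
- Log half-width, L1 against L2: t·s·√(1/n₁ + 1/n₂).

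The s and the degrees of freedom (3 × 298 − 3 = 891) are the same. At equal n both variances are 2s²/n, so the half-widths are identical. At unequal n the planned half-width is multiplied by √[(1/n₁ + 1/n₂)/(1/n₁ + 1/n_P)], which needs only the group sizes. The shared control is no obstacle, because it cancels from the ratio.

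The within-group CIs give a second route: the arms are independent, so SE(L1 − L2) = √(SE₁² + SE₂²) on the log scale.

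**2. How wide is that interval?** SE = SD·√(2/298); CI factor = exp(1.96·SE).

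| log-SD | SE | CI factor |
|---|---|---|
| 0.8 | 0.0655 | 1.137 |
| 1.0 | 0.0819 | 1.174 |
| 1.2 | 0.0983 | 1.212 |

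**3. How well do the planned summaries rank the lots?** P(better lot has the higher GMC) = Φ(ln(true ratio)/SE).

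- True ratio 1.25: ln = 0.2231; 0.2231/0.0819 = 2.72, giving 99.7% (98.8% at SD 1.2).
- True ratio 1.10: ln = 0.0953; 0.0953/0.0819 = 1.16, giving 88% (83% to 93% over the SD range).

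**4. Response rates.** A Lot 1 minus Lot 2 interval needs only the two lots' counts. Take 259/298 against 244/298 as an example:

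- Difference: 15/298 = 0.050.
- Simple SE: √[(0.869 × 0.131 + 0.819 × 0.181)/298] = 0.0297, giving −0.008 to 0.108.
- Miettinen-Nurminen interval: −0.008 to 0.109, practically the same.

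For true rates of 0.87 and 0.82, exact enumeration puts the better lot strictly ahead in 94.9% of trials, with ties in 1.1%.

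**5. Objectives against analyses.** Non-inferiority (3.1, objective 2) is handled in 8.6.1 and 8.8. The GMC ratios (3.1, objective 3, and 3.2) are handled in 8.6.1 and Table 3. Lot safety is compared with Prevnar 13 in 8.6.2. No objective in Section 3 asks for a lot-to-lot estimate, and no section makes lot selection depend on one.

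**The case for a change.** The strongest case for the concern has three parts.

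*Ranking is not inference.* With identical lots, the observed GMC ratio for a given serotype is at least 1.10-fold from 1 in 2·(1 − Φ(1.16)), about 24% of trials (15% to 33% over the SD range). Such gaps will therefore be seen somewhere among 15 serotypes. This is true. But if the lots are identical, choosing either costs nothing, and anyone who wants to know whether a gap exceeds chance can get the interval as in step 1.

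*Pass/fail may be misread as a lot comparison.* It would be a poor one. On 6B alone, identical lots at 0.82 give exactly one pass at one-sided 0.025 in 13.2% of trials, or 11.6% once the single passing lot is re-tested at 0.0125. Adding 6A and 19A, with assumed Prevnar 13 rates of 0.95 down to 0.90 and independent serotypes, the figures are 15.5% to 25.2%, or 13.5% to 20.7% after re-test. Conversely, lots at 0.87 and 0.82 on 6B both pass that serotype in 91.6% of trials. These figures stand as a caution to readers. The plan, however, nowhere uses pass/fail to choose between lots.

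*Prespecifying would prevent improvisation after the group results are seen.* There is some merit here. The freedom is small, since 8.6.1 already fixes the log scale, the pooled-variance model and the Miettinen-Nurminen method. The choice of lot is an internal development decision, to be tested in later phases, and not a claim made from this trial.

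A full set of lot contrasts would also have limited value. GMC ratios at three time points, post-dose 3 response rates, and eight Tier 1 events for four doses plus all doses combined make 45 + 15 + 40 = 100 unadjusted intervals. About 100 × 0.05 = 5 would exclude no difference by chance if the lots were identical. Power for 0.87 against 0.82 would be 39%; 80% power would need 822 per lot. Nor would the table say which lot should advance.

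The supplemental SAP is not among the documents and might contain a lot contrast; the conclusion does not depend on that.

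**Conclusion.** The concern does not hold. It is correct that the visible plan names no Lot 1 versus Lot 2 estimate, and the general wording in 8.4 and 8.9.2 should not be stretched to supply one. But the plan as written gives sound results. Its formal contrasts match its formal objectives, no inference against Prevnar 13 is affected, and no information about the lots is lost. The GMC lot ratio and its interval follow from planned output by division and, where group sizes differ, a rescaling by those sizes. Response-rate and adverse-event differences follow from per-lot counts. Benchmarking each lot against the licensed comparator is a legitimate basis for a phase II choice.

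In size: the lot-ratio interval is a factor of about 1.17 either way (1.14 to 1.21), and the better lot has the higher GMC in about 99.7% of trials at a true 1.25-fold difference and 88% at 1.10-fold. These figures assume 298 evaluable per lot and a log-SD of 1.0 (0.8 to 1.2). That the lot interval can be recovered does not depend on the SD; it requires only that group sizes and counts are reported with the planned estimates. A direct table is a matter of preference, not a correction.

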4.2.2 Rationale for Dose Selection/Regimen

4.2.2.1 Rationale for the Use of Comparator

Placebo-controlled clinical studies, for new PCVs, are no longer feasible given the proven clinical efficacy and widespread use of licensed pneumococcal conjugate vaccine worldwide. Prevnar 13™ is currently the only recommended vaccine for the prevention of pneumococcal disease in infants in the US and is also used in many other countries worldwide. It will be used as the active comparator in this trial.

4.2.3 Rationale for Endpoints

4.2.3.1 Immunogenicity Endpoints

Serum will be collected at 3 pre-specified time points during the trial:

- 1) Approximately 1 month PD3
- 2) Pre-dose 4
- 3) Approximately 1 month PD4

Sera will be used for the following measurements:

- (1) IgG responses using the Pn ECL assay.
- (2) Functional antibody activity, OPA, will be measured using the MOPA-4 assay in the first 50% of infant subjects enrolled at US investigator sites who have sufficient serum volume at PD3 to perform both the PnECL and MOPA-4 assays. OPA will be conducted at Pre-Dose 4 and PD4 for all of the subjects who had OPA performed at PD3 and for which there is sufficient volume.

There are two primary immunogenicity endpoints in this trial:

- (1) The serotype-specific IgG responses (proportion of responders achieving IgG reference level of $\geq 0.35 \mu\text{g/mL}$) induced by V114-1, V114-2, and Prevnar 13TM, by Pn ECL assay at 1 month following receipt of the third dose of the trial vaccine for the 13 serotypes shared with Prevnar 13TM.

The use of the $\geq 0.35 \mu\text{g/mL}$ threshold value has been recommended as an acceptable threshold value for evaluating the clinical performance of pneumococcal conjugate vaccines [16], [17].

- (2) The IgG GMCs for all 15 serotypes included in V114 at 1 month post-dose 3.

Other immunogenicity endpoints include:

- (1) The serotype-specific responses for V114-1, V114-2, and Prevnar 13TM, based on IgG GMCs by Pn ECL assay immediately prior (pre-dose 4) and 1 month following receipt of the fourth dose of the study vaccine for all 15 serotypes included in V114.
- (2) The serotype-specific responses for V114-1, V114-2, and Prevnar 13TM, based on the proportion of subjects meeting the serotype-specific threshold value of $\geq 0.35 \mu\text{g/mL}$ by Pn ECL assay at 1 month following receipt of the third dose of the study vaccine for the two serotypes unique to V114, and immediately prior (pre-dose 4) and 1 month following receipt of the fourth dose of the study vaccine for all 15 serotypes included in V114.

Functional antibody activity, OPA, will also be evaluated in approximately 50% of infants enrolled at US study sites with sufficient serum available at PD3 to perform both the Pn ECL assay and the OPA testing on all 15 serotypes in V114. Pre-dose 4 and PD4 OPA measurements will be conducted for all of the subjects who had PD3 OPAs performed and for which there is sufficient serum. The proportion of subjects meeting OPA titer ≥ 8 and the OPA GMTs at PD3 and separately at pre-dose 4 and PD4 will be summarized for each serotype.

Primary immunogenicity endpoints for the comparison of pneumococcal conjugate vaccines in children are based on immunoglobulin (IgG) antibodies responses. Such responses are consistent with the recommendations from the World Health Organization (WHO) and many regulatory agencies worldwide and include serotype-specific measurements of the following endpoints: a) the proportion of subjects achieving IgG antibody concentrations $\geq 0.35 \mu\text{g/mL}$ four weeks after third dose; and b) the IgG geometric mean antibody concentration (GMC) measured 4 weeks after the third and fourth doses. For new serotypes not included in licensed pneumococcal conjugate vaccine used as comparator, non-inferiority comparisons are made to the lowest response rate observed to any vaccine serotype among recipients of the licensed vaccine.

